## 5.2.2 Clinical Experience

Standard treatment for hypercholesterolemia relied on diet modification and use of statins until the introduction of antibodies, such as evolocumab, that inhibit proprotein convertase subtilisin-kexin type 9 (PCSK9). Evolocumab is an antibody that binds to PCSK9, where the antibody's therapeutic effect is to reduce LDL-cholesterol and where the therapeutic goal is to reduce risk for heart attack and stroke.

In phase II and III clinical trials (Open Label Study of Long Term Evaluation Against LDL- C [OSLER-1 and OSLER-2], respectively) evolocumab decreased LDL cholesterol by 52%, decreased total cholesterol by 36%, and raised high-density lipoprotein cholesterol by 7% when compared to standard treatment (Sabatine et al., 2015). A follow-up study (Further Cardiovascular Outcomes Research with PCSK9 Inhibition in Patients with Elevated Risk [FOURIER]) was performed to evaluate effects on reducing cardiovascular endpoints, such as myocardial infarction, stroke, unstable angina, or need for coronary revascularization. The combination of evolocumab plus standard statin therapy significantly reduced the risk of cardiovascular death, myocardial infarction, or stroke by 20%, which correlated with decreases in LDL levels. Evolocumab is currently FDA-approved for treatment of hypercholesterolemia in combination with other lipid-lowering medications (e.g., statins, ezetimibe), and is only recommended as

single- agent therapy in patients diagnosed with primary hyperlipidemia, which is typically an inherited disease. It is given as a 140-mg subcutaneous injection once every 2 weeks or 420 mg monthly .

Peak plasma concentrations occur at 3–7 days  and evolocumab has a half-life of 11–17 days and like other monoclonal antibodies, is eliminated by degradation to short peptides and amino acids. When considering adverse reactions, this has been well characterized as part of the FDA approval process. In a 52- week, double-blind, randomized, placebo-controlled trial, 599 patients received 420 mg of evolocumab subcutaneously once monthly. The mean age was 56 years (range: 22 to 75 years), 23% were older than 65 years, 52% women, 80% White, 8% Black, 6% Asian; 6% identified as Hispanic ethnicity. Adverse reactions reported in at least 3% of evolocumab-treated patients, and more frequently than in placebo-treated patients are shown in Table 1.

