#### 7.1.2 Definition of Dose-Limiting Toxicity (DLT)

Among patients treated with Evolocumab, toxicities will be graded according to the National Cancer Institute (NCI) Common Terminology Criteria for Adverse Events (CTCAE) version 5 criteria. DLTs will be defined as any of the following events that are at least (possibly, probably, or definitely) attributable to study treatment (i.e., evolocumab):

- Any Grade 3 or any Grade 4 toxicity (at least possibly, probably, or definitely attributable to study treatment [i.e., evolocumab]) that is not reversible (i.e., reversible means the toxicity is trending towards improvement and has downgraded to at least Grade 2 or back to baseline) within 2 weeks, including cerebral edema or worsening neurologic symptoms

- Any life-threatening event (at least possibly, probably, or definitely attributable to study treatment [i.e., evolocumab]) that is not reversible (i.e., reversible means the toxicity is trending towards improvement and has downgraded at least to Grade 2 or back to baseline) within 2 weeks
- Treatment-related death at least possibly, probably, or definitely attributable to study treatment (i.e., evolocumab).
- Any grade 2 or higher serious autoimmune toxicities, particularly those affecting vital organs (e.g., cardiac, renal, CNS) occurring within 2 weeks of any protocol treatment (i.e., evolocumab).

Exceptions to the above DLT definition include:

- Seizures: Due to the nature of the disease under investigation in this protocol, patients may have pre-existing seizures or be susceptible to new seizures as a result of the underlying disease process. Although seizures may be defined as Grade 3 or 4 toxicities under NCI CTC, and will be reported as such in this protocol, seizures will not be considered an unacceptable adverse event if, in the opinion of the Principal Investigator they have not increased in frequency or can be attributed to another recognized cause of increasing seizure frequency such as sub-therapeutic anti-convulsant levels or biopsy proven tumor progression.

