## 10 SCREENING AND ON-STUDY TESTS AND PROCEDURES

Table 4. Schedule of Events for Treatment Arm

Description	Screening (within 14 days of starting evolocumab)	Treatment Period	Active Follow-up Period

	Pre-Evolocumab Screening	Evolocumab Injection	Surgical Procedure	Post-Operative Visit
Day(s)		1	4-14	Typically ~2 weeks following surgery
General Evaluations				
Evolocumab Informed Consent	X 			
Physical Exam	X			X
Neurologic Exam	X			X
Adverse Events			Continuous 	
Laboratory Evaluations				
CBC with differential	X			X
CMP	X			X
Lipid profile	X			
Serum Pregnancy Test, if applicable	X 	X 		
Pharmacokinetic blood draws (5 mL) 		X	X*	
Tumor tissue analysis (estimated >20mg available) 			X	
Treatment				
Evolocumab		X		

\* This blood sample taken at time of surgery or biopsy so that drug level in the blood can be compared to intratumoral concentration.

**Table 4** shows the schedule of events for the treatment arm of this study, including all study-related general evaluations, laboratory evaluations, disease evaluations, and treatments. Of particular importance for this phase 1 study are the tumor sampling and pharmacokinetic blood draws to investigate evolocumab concentration profiles following agent administration. Patients who consent to participate as a control will only be asked to have the following:

- Informed consent on the control consent form
- PK blood draw prior to surgical procedure
- Tumor tissue analysis, if available

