## 10.4 Active Follow-up Period

### Days 4-14 – Surgical resection or biopsy

- Tumor tissue collection (applies to patients who consent to either arm of the study) – this tissue will be taken intraoperatively for pharmacokinetic LC-MS analysis to assess for the presence of evolocumab.
  - Sample will only be taken for analysis if greater than 20 mg of resected or biopsied tissue available (excess available beyond that required for histological analysis)
  - Sample to be aliquoted into 25 mg sections for resections and 10-20 mg (1-2 cores) for biopsies

Treatment arm only:

- Pharmacokinetic blood draw (5 mL, drawn at time of surgery or biopsy, i.e., PK draw may occur either immediately before or during surgery or biopsy)Error! Bookmark not defined.
- Adverse events monitoring

About 2 weeks following surgery or biopsy (treatment arm only)

- Physical and neurological exam
- Laboratory evaluations (obtained as part of standard post-operative labs)
  - CBC with differential
  - CMP
- Adverse events monitoring

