## **10.5 End of Treatment**

Once the baseline PK blood draw is collected (both arms) and the evolocumab injection (treatment arm only) is completed, the treatment phase of the study is over and the active follow-up period begins. During the active follow-up period (see Section 10.4), patients undergo their standard of care surgical resection or biopsy with tissue collection, if available. Patients in the treatment arm return for post-surgical wound care about 14 days post-surgical procedure **as needed per standard neurosurgical practice**.

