## **10.6 Follow-up Period**

Once active follow-up is complete, patients are followed per standard of care. The study team will review medical records of patients enrolled in the treatment arm to collect information for ongoing serious adverse events and new onset serious adverse events for up to 30 days following Evolocumab injection. If patients subsequently undergo additional biopsy or resection, a sample of leftover tissue may be requested for analysis.

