### **10.9.2 Physical Exam**

Vital signs and physical and neurologic examinations will be assessed for patients in the treatment arm and recorded prior to enrollment and at each visit according to Table 4.

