## **11 SAFETY MONITORING AND REPORTING**

The PI is responsible for the identification and documentation of adverse events and serious adverse events, as defined below. Among patients receiving evolocumab and at each study visit, the PI or designee must assess, through non-suggestive inquiries of the subject or evaluation of study assessments, whether an AE or SAE has occurred.

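### The two-week autoimmune DLT window closes before the first scheduled post-dose exam and blood tests, all of which follow surgery

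*Combined protocol and SAP*

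**What the plan says.** The fourth DLT bullet in Section 7.1.2 covers serious autoimmune toxicity of Grade 2 or higher, "particularly those affecting vital organs (e.g., cardiac, renal, CNS) occurring within 2 weeks of any protocol treatment". The lead-in to the list requires at least possible attribution to evolocumab. Under Section 11.1.2 any DLT pauses the study for review.

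Section 7.1 places surgery or biopsy 4-14 days after the single injection. In Table 4 the physical exam, neurologic exam, CBC and CMP appear twice for treated patients: at screening and at the post-operative visit, timed "Typically ~2 weeks following surgery". Section 10.4 agrees and takes the blood results from routine care: "Laboratory evaluations (obtained as part of standard post-operative labs". On the day of the procedure it lists tissue collection, a PK draw and adverse event monitoring. Section 10.9.2 adds no further exam, because exams are "recorded prior to enrollment and at each visit according to Table 4".

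Section 10.5 says treated patients return for wound care about 14 days after the procedure "as needed per standard neurosurgical practice". Table 4 and Section 10.4 list the post-operative assessments without that qualifier.

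Other routes to an event also exist. Table 4 marks adverse events as continuous. Section 11 requires assessment at each study visit "through non-suggestive inquiries of the subject or evaluation of study assessments". Section 10.6 has the team review medical records for ongoing and "new onset serious adverse events for up to 30 days following Evolocumab injection".

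**The concern.** A time-limited safety criterion works best when something scheduled inside the window can show the event. Here nothing scheduled does so for a finding that depends on an exam or a chemistry result. Renal and CNS toxicity, two of the three organs the bullet names, are of that kind when symptoms are slight or absent.

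Three practical consequences follow. First, such a finding made at the post-operative visit counts under this bullet only if its onset is placed at least several days earlier, and the plan gives no rule for doing that. Second, every scheduled post-dose reading comes after a craniotomy or biopsy, so there is none taken on drug but before the procedure to help separate a drug effect from a surgical one. The control arm cannot supply that contrast: it has no screening tests and leaves the study after tissue collection. Third, if the wording in Section 10.5 were applied to the whole visit, the only post-dose exam and blood tests could be skipped.

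**Working it through.** The plan states no figure on this point, so there is none to reproduce. The check is date arithmetic.

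**Inputs**
- Autoimmune DLT window: 14 days after injection (Section 7.1.2).
- Injection to procedure: 4-14 days (Section 7.1).
- Procedure to post-operative visit: about 14 days (Table 4, Sections 10.4 and 10.5).
- Record review for serious events: 30 days after injection (Section 10.6).

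**First scheduled post-dose exam, CBC and CMP** = (injection to procedure) + (procedure to visit)
- Earliest: 4 + 14 = 18 days. Latest: 14 + 14 = 28 days.
- Past the window: 18 − 14 = 4 days to 28 − 14 = 14 days.
- With Table 4's numbering (injection = Day 1, procedure on Days 4-14), the procedure is 3-13 days after injection. The visit is then at 3 + 14 = 17 to 13 + 14 = 27 days, which is 3-13 days past the window.

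**Sensitivity to the approximate visit timing.** The plan gives no tolerance. Assume 10-18 days after the procedure.
- Range: 4 + 10 = 14 to 14 + 18 = 32 days (13-31 with Day 1 numbering).
- Only the earliest procedures combined with an early visit reach the window.

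**Latest visit that would still fall inside the window** = 14 − (injection to procedure)
- Procedure at 4 days: 10 days after it. At 7 days: 7 days after it. At 14 days: 0 days after it.
- So for a procedure at 14 days, the whole two-week post-operative follow-up in Section 7.1 lies outside the criterion.

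**The same dates under the fix**
- A reading on the day of the procedure falls 4-14 days after injection (3-13 with Day 1 numbering), inside even the present window. A routine result up to 48 hours older is at least 4 − 2 = 2 days after injection (3 − 2 = 1 with Day 1 numbering), so it is still post-dose.
- The nominal visit at 18-28 days falls inside a 30-day window. For a procedure at 14 days it stays inside if held within 30 − 14 = 16 days of the procedure.

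**The case against.** The case against is substantial, and most of it stands.

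- **The bullet is limited to serious toxicity.** Read with the definition in Section 11.2, a silent laboratory change would seldom qualify, and Section 11.1 does not record clinically insignificant abnormalities as adverse events. This narrows the point considerably.
- **The window governs onset, not detection.** An event found on day 20 can be dated to day 12 on clinical grounds. That is correct. What remains is that the plan schedules no in-window reading to base the dating on.
- **Serious events have their own capture.** The record review in Section 10.6 does not depend on the post-operative visit, and the procedure itself brings treated patients under adverse event monitoring 4-14 days after dosing. A reader might infer that autoimmune DLTs would go unseen altogether; the documents do not support that.
- **Little turns on the DLT label.** There is one dose, no escalation and no boundary on the number of DLTs. Section 7.1.4 pauses the study for any observed reaction, and Sections 7.1, 11.1.2 and 12.1 add further triggers without this window. A reader might infer that the study could wrongly continue after a known event; the overlapping triggers point the other way.
- **The qualifier in Section 10.5 is attached to wound care.** That this is the same visit as in Table 4 is an inference from the matching arm and timing. A reader might conclude that the safety assessments are optional. The documents show only an inconsistency in wording.

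One further tempting argument fails. Section 5.2.2 says "evolocumab has a half-life of 11–17 days", so drug is still present when the window closes, but nothing in the plan links residual drug level to autoimmune risk. It gives no measure of missed events.

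**Conclusion.** The mismatch is real and its consequence is minor. At nominal timing no scheduled post-dose exam, CBC or CMP falls inside the two-week window: they come 4-14 days too late (3-13 with Day 1 numbering), and all of them follow surgery. The effect is confined to detecting, attributing and classifying autoimmune toxicity that shows itself by exam or laboratory test. It does not extend to symptomatic or serious events in general, to the decision to pause once an event is known, or to the PK and PD results.

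The conclusion rests on reading the approximate two weeks as 14 days, and on treating the wound-care return as the Table 4 visit. The timing gap does not depend on the second assumption. No event rate is assumed, because the documents give none for this toxicity in this population. Routine peri-operative tests may narrow the gap in practice, but the plan does not require them to be done or recorded before the post-operative visit.

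**What to change.** 1. In the fourth bullet of Section 7.1.2, replace the two-week limit with: from injection through 30 days after injection. This matches the serious event follow-up already in place. Keep the requirement of at least possible attribution to evolocumab.
2. In Table 4 and Section 10.4, for treated patients, record a neurologic exam, CBC and CMP before the procedure on the day of surgery or biopsy, accepting routine pre-operative results from the previous 48 hours. Do not rely on the PK sample for this: Section 10.4 allows that draw during the procedure, and its tube type is still to be decided.
3. In Section 10.5, state that the Table 4 post-operative assessments are required even when a wound-care return is not needed.

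Leave every pause trigger at its present threshold.

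The cost for 10 treated patients is at most 10 lab sets and 10 neurologic exams, mostly routine already, plus wording changes. No patients are added. The drawback is that a longer window takes in some post-surgical events, including neurologic ones, that will need a judgment on attribution. The pre-procedure reading in item 2 gives that judgment something to rest on.

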- New neurologic deficits: Due to the nature of the disease under investigation in this protocol, patients may develop new neurologic deficits as a result of tumor invasion. A new neurologic deficit, which resolves within 2 weeks after initiation of medical therapy, will not be considered an unacceptable adverse event. New neurological symptoms will not be an unacceptable adverse event if they can be ascribed to tumor progression (e.g. documented with histopathologic analyses of biopsy tissue; or; they respond to treatment (e.g., oral steroids, within 2 weeks)).
- Thromboembolism: Due to the high incidence of deep vein thrombosis (DVT) in this patient population, patients may have undiagnosed pre-existing DVTs or be susceptible to the development of DVTs due to the underlying disease process. Although DVT may be defined as Grade 3 or 4 toxicities under NCI CTC, and will be reported as such in this protocol, DVT will not be considered unacceptable adverse event in this protocol.
- Syndrome of Inappropriate Antidiuretic Hormone (SIADH): Due to the high incidence of SIADH in this patient population, patients may be susceptible to the development of SIADH due to the underlying disease process. Although SIADH may be defined as Grade 3 toxicity under NCI CTC, and will be reported as such in this protocol, SIADH will not be considered an unacceptable adverse event in this protocol unless it is refractory to medical management.
- Muscle Weakness and Weight Gain: Due to the high incidence of muscle weakness and weight gain in patients taking steroids, patients may be susceptible to the development of muscle weakness or weight gain, which is due to steroids alone. Although muscle weakness may be defined as Grade 3 or Grade 4 toxicity and weight gain  $\geq 20\%$  may be defined as Grade 3 toxicity under NCI CTC, and will be reported as such in this protocol. Muscle weakness or weight gain will not be considered an unacceptable adverse event in this protocol if the patient has required steroids greater than physiologic doses in the interval between the immunization and the development of the toxicity.

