- Tumor Progression: Due to the nature of the disease under investigation in this protocol, patients may have an increase in pre-existing neurologic deficits or have an onset of new neurologic deficits due to tumor progression. Although such neurologic deficits may be defined as unacceptable adverse events under NCI CTC, and will be reported as such in this protocol, these clinical changes are not an unexpected phenomenon in this disease in the setting of tumor growth. As a result, neurologic deficits will not be considered an unacceptable adverse event if unequivocal tumor progression can be documented radiographically or histologically.
- Immune Related Exceptions: grade 2 Pneumonitis; grade 2 or 3 colitis or diarrhea; grade 2, 3, or 4 endocrinopathies (including but not limited to hypophysitis, adrenal insufficiency, hyperthyroidism, and type 1 diabetes mellitus). Any of the aforementioned immune-related AEs will not be considered unacceptable if the event resolves to Grade 1 after withholding therapy.

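### Section 7.1.2 lets an undefined response to steroids ascribe a new neurologic deficit to tumor progression, so a partial responder still at Grade 3/4 can fall outside the DLT definition

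*Combined protocol and SAP*

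**What the plan says.** Section 7.1.2 makes a Grade 3 or 4 toxicity at least possibly attributable to evolocumab a DLT if it is not reversible within two weeks, "including cerebral edema or worsening neurologic symptoms". It defines the key word: "reversible means the toxicity is trending towards improvement and has downgraded to at least Grade 2 or back to baseline". A list of exceptions follows, and two of them concern this point.

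- **New neurologic deficits.** The first exemption rests on resolution: "A new neurologic deficit, which resolves within 2 weeks after initiation of medical therapy, will not be considered an unacceptable adverse event". The next sentence excuses new neurological symptoms if "they can be ascribed to tumor progression (e.g. documented with histopathologic analyses of biopsy tissue; or; they respond to treatment". The bracketed detail on treatment is "they respond to treatment (e.g., oral steroids, within 2 weeks".
- **Tumor Progression.** This exception recognizes that "patients may have an increase in pre-existing neurologic deficits or have an onset of new neurologic deficits due to tumor progression", and states that "neurologic deficits will not be considered an unacceptable adverse event if unequivocal tumor progression can be documented radiographically or histologically".

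Sections 7.1.1 and 11.1.2 both pause the study when a DLT occurs.

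**The concern.** Two exceptions excuse the same kind of event on very different evidence. One asks for unequivocal progression on imaging or histology. The other accepts that the symptom responded to treatment, with a time limit but no grade, no resolution and no return to baseline.

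Response to steroids is weak evidence that progression is the cause. Section 7.1.6 describes steroids as treatment for swelling and mass effect, and cerebral edema is named in the first DLT criterion. A steroid response could therefore follow either from the tumor or from drug-related edema, and does not separate them.

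What is at stake is whether the pause is automatic. If the event is not a DLT, a pause depends on whether someone judges the toxicity significant (Sections 7.1 and 11.1.2), a term the protocol does not define.

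**Working it through.** The plan gives no figure to reproduce here. The check sets the provisions side by side and then counts the cases in which the clause changes the answer.

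**One event traced through Section 7.1.2.** Take a new Grade 4 symptom, at least possibly attributable to evolocumab, that improves to Grade 3 on oral steroids within two weeks, with no imaging or tissue evidence of progression.

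| Provision | Test | Met? | Result |
|---|---|---|---|
| First DLT criterion | Grade 3/4 and not down to Grade 2 or baseline in two weeks | Yes | DLT |
| New deficits, resolution sentence | Resolved within two weeks of starting therapy | No | Not excused |
| New deficits, response clause | Responded to treatment within two weeks | Yes, if partial response counts | Excused |
| Tumor Progression exception | Unequivocal progression documented | No | Not excused |

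The response clause alone removes this event from the DLT definition.

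**How often the clause decides.** For a new attributable Grade 3/4 symptom, cross three factors: status at two weeks (resolved; Grade 2 or baseline; still Grade 3/4), documented progression (yes/no) and steroid response (yes/no). That gives 3 × 2 × 2 = 12 combinations. Therapy is assumed to start at onset, so that the two-week windows coincide.

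- *Respond* includes partial improvement. With the clause, a DLT needs still Grade 3/4, no documented progression and no response: 1 × 1 × 1 = 1 combination. Without it, response no longer matters: 1 × 1 × 2 = 2. Change: 2 − 1 = 1 of 12.
- *Respond* means *resolve*. A symptom still at Grade 3/4 cannot satisfy the clause, so there are 2 DLT combinations with it and 2 without. Change: 0 of 12.
- *Respond* means *reversible* as defined in the section. Again 2 and 2. Change: 0 of 12.

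The muscle-weakness exception is a separate route for some motor deficits. It applies "if the patient has required steroids greater than physiologic doses in the interval between the immunization and the development of the toxicity". The study gives no immunization, so this presumably means the evolocumab dose. Adding it as a fourth yes/no factor gives 24 combinations. Where it applies, the event is excused with or without the clause, so the changes are 1, 0 and 0 of 24.

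These are counts of logical cases, not probabilities. They cover the Grade 3/4 reversibility criterion only.

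**Which reading is natural.** The sentence just before already exempts deficits that resolve within two weeks of starting therapy. If *respond* meant the same, the clause would add nothing. A different word in the next sentence, with no reference to resolution or to the defined term *reversible*, most naturally covers something less than resolution.

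**The case against.** **The exceptions do not contradict each other.** A reader might infer that Section 7.1.2 gives two incompatible answers for one event. It does not. The Tumor Progression exception says *if*, not *only if*. It is one sufficient route in a list of alternatives, and satisfying another route without it is how such a list works. This stands. What remains is that the looser route makes the stricter standard avoidable.

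**Clinical ascription is still required.** Treatment response sits inside an *e.g.* bracket illustrating how symptoms may be ascribed to progression, so an investigator could decline to ascribe. That is true, but the text offers response beside histology as adequate support. If the odd punctuation instead makes response a free-standing alternative, an undefined response still excuses the event.

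**Steroid response is a clinical matter.** Section 7.1.6 restricts steroids because of immune monitoring and says nothing about attribution, and edema and mass effect also fit tumor effects. This stands as far as it goes. The point needs only that response does not discriminate between the two causes.

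**Other safeguards remain.** A reader might infer that such an event would go unseen. It would not: AE recording and weekly review (11.1.2), immediate SAE reporting to the PI (11.2.1) and action on an unexpected frequency of Grade III/IV events (12.1) all continue. Section 7.1.4 also promises a pause if any reactions are observed, though its context is immunologic reactions. With one dose per patient and no escalation, classification cannot alter the affected patient's dosing. These facts keep the point small. None of them is an automatic pause for this event.

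**Defining *respond* would be enough.** Tying it to *reversible* would close the Grade 3/4 gap. For those events, however, the clause would then repeat the base rule, so deletion is simpler.

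**Conclusion.** The point holds as a minor weakness in the DLT definition. On the natural reading, the response clause excuses one kind of event that the base rule would count: new, neurologic, Grade 3/4, at least possibly attributable to evolocumab, partly improved on treatment, still Grade 3/4 at two weeks, without documented progression, and outside the other exceptions. If *respond* is taken to mean *resolve*, nothing turns on the clause.

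It would be tempting to attach a probability to an affected pause in the 10-patient arm. The documents do not support one. They give no rate for this event, and the adverse reaction tables in Section 5.2.2 come from lipid trials and do not bound possibly attributable neurologic events in glioma patients. Any such figure would restate an assumed rate. Nor does the point reach the primary PK comparison or any other endpoint or planned analysis. It concerns DLT classification and the pause rule only.

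**What to change.** In the New neurologic deficits exception, delete the clause on response to treatment and have the sentence say, in substance: *New neurological symptoms are exempt when progression as their cause has been documented radiographically or histologically, to the standard of the Tumor Progression exception below.* Keep the exemption for a new deficit that resolves within two weeks of starting medical therapy, and leave the Tumor Progression exception unchanged.

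The cost is one sentence in one section. The revised sentence will largely duplicate the Tumor Progression exception, which does no harm. Table 4 schedules no imaging and none need be added, because documentation would come from clinical imaging or histology. It follows that classification can depend on whether such evidence exists. Without it, an attributable event still at Grade 3/4 at two weeks, and not otherwise excepted, counts as a DLT and is reviewed, which is the cautious direction. The downside is possibly an extra pause for review.
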